1 RESEARCH REFERENCE NUMBERS

Sponsor Protocol Number:	PID 16663
Clinical Trials Unit (CTU)	OCTRU221
Reference:	
Funder Reference:	17/150/01
Ethics Reference Number:	23/SC/0012
IRAS Number:	315065
Registry:	International Standard Randomised Controlled Trial Number (ISRCTN): ISRCTN17249875

5 LAY SUMMARY/PLAIN ENGLISH SUMMARY

The PART study aims to test whether treating only the part of the prostate containing the prostate cancer is as effective in curing prostate cancer as treating the whole prostate gland, and has fewer side effects. Treatment of the whole prostate gland (known as 'radical' treatment) includes surgical removal, radiotherapy, or brachytherapy.

Prostate cancer is the most common cancer in men in the UK. Treatment of the whole prostate ('radical' treatment) is normally offered, even if the cancer is only on one side of the prostate gland. New technologies can now treat the part of the prostate affected by the cancer only (known as 'partial ablation', or PA), destroying the cancer but preserving urinary and sexual functions. PA shows promising results in terms of having minimal side effects in men with low-risk prostate cancer, compared to a policy of 'active surveillance' (i.e. no active treatment). We want to test PA in men with intermediate-risk unilateral localised prostate cancer, who would usually be advised to have radical treatment.

The two types of PA in this trial will be Irreversible Electroporation (IRE) and High Intensity Focal Ultrasound (HIFU). NICE currently recommends that both HIFU and IRE as PA treatments for prostate cancer are safe, and that more evidence is needed to assess their efficacy (https://www.nice.org.uk/guidance/ipg756) (https://www.nice.org.uk/guidance/IPG768). IRE is an image-guided tissue ablation technology that induces cell death via short, strong pulsed electric fields. Due to its non-thermal nature, IRE preserves vessels, nerves and extracellular matrix, making it a suitable PA treatment modality for prostate cancer. HIFU uses ultrasound energy focused by an acoustic lens to cause tissue damage as a result of thermal coagulative necrosis and acoustic cavitation. The results of the PART study will inform recommendations for widespread use of PA throughout the NHS; currently, IRE and HIFU are available at only a few specialist centres.

We aim to recruit 800 men from 10+ hospitals in the UK. Participants will be randomly allocated to either radical treatment (choice of surgery or radiotherapy or brachytherapy, as most appropriate) or PA treatment (IRE or HIFU). All patients will be assessed regularly to check if the treatments have worked, using blood tests and (for the PA arm) repeat imaging and prostate biopsies. If there is any

sign of the disease returning or worsening, additional treatments will be discussed and offered. We will compare how well the treatments work by measuring the time it takes for additional treatment to be necessary in the radical treatment arm, or to require treatment of the whole prostate gland, or other prostate cancer-specific treatment, in the PA arm. We will also assess quality of life using questionnaires, and costs to the NHS of each treatment.

6 STUDY SYNOPSIS

Full Study Title:	A randomised controlled trial of Partial prostate Ablation versus Radical Treatment in intermediate risk, unilateral clinically localised prostate cancer
Short Title:	Partial prostate A blation versus R adical T reatment
Study Acronym:	PART
Study Design:	The PART study is a multi-centre, two arm, parallel design, randomised controlled clinical study.
	A QuinteT Recruitment Intervention (QRI) is incorporated into the study to identify and understand any challenges to recruitment.
Study Participants/Target Population:	The PART study will recruit patients aged 18 years and over with localised intermediate-risk prostate cancer amenable to either partial ablation of the prostate or radical treatment (radical prostatectomy, radical radiotherapy, or low dose-rate brachytherapy).
Eligibility criteria:	 Inclusion: 1. Age ≥18 years with unilateral clinically significant intermediate-risk Gleason Grade Group 2 or 3 (3+4 or 4+3) PCa, or dominant unilateral clinically significant intermediate-risk PCa and contralateral low-risk low-volume Gleason Grade Group 1 (3+3) PCa 2. PSA ≤ 20 ng/ml within the last 120 days 3. Pre-biopsy mpMRI scan within the previous 6 months, and bilateral biopsies of the prostate (transrectal or transperineal, and targeted biopsy for visible lesions) 4. Clinically ≤T2b intermediate-risk Gleason Grade Group 2 or 3 (3+4 or 4+3) disease judged by results of digital rectal examination, imaging by Multi-parametric Magnetic Resonance Imaging (mpMRI) and biopsy (low-risk Gleason Grade Group 1 lesions on the contralateral side are acceptable) 5. Fit, eligible, with a standard-of-care recommendation for any or all of radical prostatectomy, radical radiotherapy or low dose-rate brachytherapy (LDR-B), and suitable for PA using at least one of irreversible electroporation (IRE) or high intensity focused ultrasound (HIFU)

6.	An understanding of the English language sufficient to receive
	written and verbal information about the study, its consent
	process and complete study questionnaires
Exc	clusion:
1.	Taking part in another therapeutic prostate cancer clinical trial or
	has been involved in such trials within the previous 4 months (NB.
	the TRANSLATE trial is a diagnostic trial and co-enrolment is
	permitted)
2.	PSA > 20ng/ml within the last 120 days
3.	Unfit for radical treatment or general anaesthesia or cannot
	tolerate transrectal ultrasound
4.	In the opinion of the treating physician, has a contraindication to
	either HIFU or IRE
5.	Not suitable for mpMRI or have a single or bilateral hip
	replacement
6.	Has evidence of extraprostatic extension by mpMRI, or clinical or
	radiological ≥T3 disease
7.	Concomitant cancer or previous active treatment for PCa
8.	Evidence of metastatic disease
	Bilateral intermediate-risk disease or higher
10	Low-risk (Gleason Grade Group 1) disease only, or high-risk (Grade
	Group ≥4) PCa only
11	History of acute urinary retention within the last 6 months prior to
	entry to the study
12	Prostatic calcification and cysts causing ultrasonic shadowing of
	greater than 1cm
13	History (within 3 years) of inflammatory bowel disease or any
	condition that may increase the risk of recto-urethral fistula
	formation
14	Has known hypersensitivity to pancuronium bromide, atricurium
	or cisatricurium, or any medical condition such that muscle
	relaxation cannot be administered as part of a general anaesthetic
	Has a history of bladder neck contracture
16	Had active treatment for a malignancy within 3 years, including
	malignant melanoma, except other types of skin cancer
	Has any active implanted electronic device (e.g., pacemaker)
	Is unable or unwilling to be catheterised
	Has had prior or current PCa therapies
20	Has had prior transurethral prostatectomy (TURP), urethral
	stricture surgery, urethral stent or prostatic implants
	Has had prior major rectal surgery (except for haemorrhoids)
22	Is actively bleeding, is anticoagulated or on blood thinning
	medications that cannot be stopped for the peri-operative period
	for a PA procedure, or has a significant bleeding disorder that may
	affect the peri-operative period as judged by the clinical staff.
23	 Unable to give consent to participate in the trial as judged by the clinical staff
24	Wishing to maintain future fertility

No. of study arms:	2		
Intervention:	Partial Ablation of the prostate (using either irreversible		
	electroporation (IRE) or high intensity focused ultrasound (HIFU))		
Comparator:	Radical prostate cancer treatment using one of the standard NHS		
	treatment options:		
	Radical prostatectomy (RP)		
	Radical radiotherapy (RRT)		
	Low dose-rate brachytherapy (LDR-	В)	
Planned Sample Size:	800 participants		
Target no. of centres:	10+		
Planned recruitment	Recruitment is expected to last for !	5 years.	
duration:		,	
Planned study duration	Feb 2023 – Mar 2030		
Duration of	Participants will receive treatment	for their prostate cancer in	
intervention/treatment:	accordance with their randomised a	-	
	standard clinical care pathways. Tre	atment should commence within	
	12 months of randomisation.		
Follow-up duration:	Participants will be followed-up in the study for as long as the study		
·	remains open – for those recruited early in the study this may be for 5		
	years post-randomisation. The study team will also seek funding to see if longer term follow-up (up to 15 years post-randomisation) may		
	possible.		
	The minimum 'on study' follow-up for the last recruited patient is 12		
	months. All participants will continue NHS follow-up beyond the		
	duration of the study.	·····	
	Objective	Outcome Measure	
Co-primary objectives	To determine whether partial	Primary treatment failure (as	
and outcome measures:	ablation provides effective	defined in section 8.5)	
	oncological outcomes compared		
	with radical treatment		
	To determine whether partial	Health-related quality of life	
	ablation has a reduced side effect	(HRQoL) as measured by the	
	profile, and an improved patient-	Patient Oriented Prostate Utility	
	reported outcomes profile,	Scale (PORPUS-P).	
	compared with radical treatment		
Secondary objectives	Refer to the main OBJECTIVES AND OUTCOME MEASURES section of		
and outcome measures:	the protocol for full study objectives and outcome measures.		
and outcome medsures.			

ABBREVIATIONS

Adverse Event	
Chief Investigator	
Consolidated Standards of Reporting Trials	
Case Report Form	
Clinical Trials Unit	
Data and Safety Monitoring Committee	
Deep vein thrombosis	
Expanded Prostate Cancer Index Composite	
Good Clinical Practice	
General Practitioner	
Hospital Episode Statistics	
High Intensity Focal Ultrasound	
Health Research Authority	
Health-related Quality of Life	
Informed Consent Form	
Irreversible Electroporation	
Investigator Site File	
International Standard Randomised Controlled Trials Number	
Low Dose-Rate Brachytherapy	
Multi-disciplinary team	
Memorial Anxiety Scale for Prostate Cancer (MAX-PC)	
Medical Dictionary for Regulatory Activities	
Mixed Models for Repeated Measures	
Magnetic Resonance Imaging	
National Health Service	
National Institute for Health and Care Excellence	
National Institute for Health and Care Research	
Oxford Clinical Trials Research Unit	
Oxfordshire Prostate Cancer Support Group	
Partial Ablation	
Partial Ablation versus Radical Treatment	
Prostate Cancer	
Pulmonary Embolism	
Principal Investigator	
Participant Identification Centre	
Participant Inormation Portal	
Patient information sheet	
Patient Oriented Prostate Utility Scale-Psychometric	
Patient and Public Involvement	
Patient-reported Outcome Measure	
Prostate-Specific Antigen	
Quality Assurance	
Quality-adjusted life year	
QuinteT Recruitment Intervention	

RCT	Randomised Controlled Trial
REC	Research Ethics Committee
RITA	Radiofrequency Interstitial Tissue Ablation
RP	Radical Prostatectomy
RRT	Radical Radiotherapy
SAE	Serious Adverse Event
SAP	Statistical Analysis Plan
SITU	Surgical Intervention Trials Unit
SOP	Standard Operating Procedure
SUSAR	Suspected Unexpected Serious Adverse Response/Reaction
SWAT	Study Within a Trial
TIDieR	Template for Intervention Description and Replication
TMF	Trial Master File
TMG	Trial Management Group
TSC	Trial Steering Committee
TURP	Transurethral Prostatectomy
VTP	Vascular Targeted Photodynamic Therapy

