8.3 Secondary objectives and outcome measures

Objective	Outcome measure	Time point(s) of evaluation of this outcome measure (if applicable)
1. To compare the effect on HRQoL of both treatment arms	HRQoL using standard, validated patient-reported outcome measures (PROMs) questionnaires: IPSS, EQ-5D-5L, EPIC and MAX- PC (Modified 18 item)	Baseline, 6wks post- treatment and 3mths, 6mths, 12mths post-randomisation, thereafter every 12 months until the end of the study.
2.To compare the effect on health care resource	Health care resource utilisation and cost-effectiveness in terms	Baseline, 3mths, 6mths, 12mths post-randomisation,

		· · · · · · · · · · · · · · · · · · ·
utilisation of both treatment arms	of cost per quality-adjusted life year (QALY)	thereafter every 12 months until the end of the study.
3.To compare the short and medium term serious adverse events related to treatments in both treatment arms	Short, medium and long-term serious adverse events related to treatments	Short term: 31 days Medium term: 3 years
4.To determine the proportion of patients needing repeat partial ablation treatment	Proportion of patients needing repeat PA treatment in the PA group	Documentation of the need for repeat PA treatment in the PA group – at 1 year post- treatment and 3 years post- treatment (for those that reach this time point in the study's lifetime)
5.To evaluate the accuracy of current mpMRI imaging and biopsy protocols in determining suitability of patients for PA	The proportion of prostatectomy patients who develop high-risk disease or bilateral intermediate disease	After histopathological evaluation (only in men who have had RP, including salvage RP)
6.To determine disease progression beyond the prostate, including local spread and development of metastases	Time to disease progression (including local and distal recurrence)	At a minimum 12 months post-randomisation follow-up of the last recruited participant, but will be longer for those recruited early in the study.
7.To determine medium-term disease-specific and overall mortality	Time to disease-specific and overall mortality	At a minimum 12 months post-randomisation follow-up of the last recruited participant, but will be longer for those recruited early in the study.

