14.7 Participants who lose capacity during the study

Participants that lose capacity during the study will be withdrawn from the study.

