16.8 Withdrawal

Withdrawal of consent means that a participant has expressed a wish to withdraw from the study altogether, or from certain aspects of the study only. The type of withdrawal will be collected on the CRF labelled 'Withdrawal'.

Participants may also be withdrawn from the study (or aspects of the study) by their clinician if they believe the participant needs to be withdrawn.

PART_Protocol_V3.0_15May2024_Clean.docx Page **49** of **77**

The Withdrawal CRF should be completed to document the reasons for withdrawal, and state who made the decision to withdraw. Discussions and decisions regarding withdrawal should be documented in the participant's medical notes. Investigators should continue to follow-up any SAEs and should continue to report any SAEs to resolution in the CRF in accordance with the safety reporting section.

Where a participant expresses a wish to withdraw from the study, the study team will determine which aspect(s) of the study the participant wishes to withdraw from; all other aspects of the study/follow-up will be continued.

The aspects of the study that the participant may request to withdraw from are as follows:

- No longer willing to receive study intervention
- No longer willing to complete study questionnaires
 - This refers to the health-related quality of life questionnaires and health care use questionnaires sent directly to participants by the study office
- No longer willing to take part in qualitative aspects of study
 - This refers to the interview for the QuinteT Recruitment Intervention/ the "Information Study"
- No longer willing to provide study tissue samples
 - This refers to any follow-up biopsies
- No longer willing to have study MRIs
- No longer willing to attend study visits
- No longer willing to be contacted by the research team to obtain CRF/outcome data
- No longer willing to have standard of care data from the medical record provided to the study
- No longer willing for standard of care data from Health data providers e.g. NHS digital, to be provided to the study

Where a participant wishes to withdraw from all aspects of study participation detailed above, this will be recorded on the Withdrawal CRF as full withdrawal.

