Completion of the Withdrawal CRF will trigger a notification to the Study Office. Appropriate action will be taken by the study teams (centrally at the study office and by the local research team at each participating site) to ensure compliance with the participant's withdrawal request. This may include marking future CRFs as not applicable and ensuring any relevant communications which the participant had consented to receive regarding their participation are no longer sent.

Data collected up to the point of withdrawal will be used in the study analysis.

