18.2 Definition of Serious Adverse Events

A serious adverse event (SAE) is any untoward medical occurrence that:

- Results in death
- Is life-threatening
- Requires inpatient hospitalisation or prolongation of existing hospitalisation
- Results in persistent or significant disability/incapacity
- Consists of a congenital anomaly or birth defect
- Is otherwise considered medically significant by the Investigator

PART_Protocol_V3.0_15May2024_Clean.docx Page **51** of **77**

Significant medical events are medical events that may jeopardise the participant and may require an intervention to prevent one of the outcomes listed above.

NOTE: The term "life-threatening" in the definition of "serious" refers to an event in which the participant was at risk of death at the time of the event; it does not refer to an event which hypothetically might have caused death if it were more severe.

Seriousness vs severity

A distinction is drawn between serious and severe AEs. Severity is a measure of intensity whereas seriousness is defined using the criteria above. Hence, a severe AE need not necessarily be serious.

18.3 Reporting of Serious Adverse Events (SAEs) from sites to the central study team

Only serious adverse events considered by the site investigator to be related (possibly, probably or definitely) to any of the study procedures and in the opinion of the Principal Investigator are considered unexpected for the study procedure will be collected in the study. Such events must be reported within 24 hours to the central study team using the SAE form within the REDCap study database. Refer to section 18.6 regarding expectedness assessment.

Treatment complications listed in section 18.4 should not be reported on a SAE form unless the complication is (in the opinion of the site investigator) considered more severe in nature than might be expected, or unexpected, for the particular intervention received. For participants undergoing IRE or HIFU treatment, the user manual for the devices should also be referred to when making an assessment of expectedness.

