19.5 Inclusion in analysis

All analyses will be on an intention-to-treat basis. This means that patients will be analysed as they are randomised irrespective of the treatment actually received. The intention-to-treat population will include all patients who have given their informed consent and for whom there is confirmation of successful allocation of a randomisation number.

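### Section 14.7 withdraws every man who loses capacity from the study, so his later failure, progression and death go uncollected, although section 16.8 already provides for partial withdrawal

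*Protocol*

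**What the plan says.** The general duration of follow-up is in the Protocol synopsis (section 6): "Participants will be followed-up in the study for as long as the study" remains open.

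Protocol section 14.7 consists of one sentence: "Participants that lose capacity during the study will be withdrawn from the study". It makes no exception for data that can be read from routine records.

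Section 16.8 states the consequence: "Data collected up to the point of withdrawal will be used in the study analysis". It adds that future CRFs may be marked as not applicable once the Withdrawal CRF is completed.

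Section 16.8 also treats withdrawal as divisible. It lists as separate items the study intervention, questionnaires, qualitative work, follow-up biopsies, study MRIs, study visits, contact for outcome data, routine medical-record data, and data from health-data providers. Whatever the man does not ask to leave continues. Withdrawal started by the clinician is divisible too: "Participants may also be withdrawn from the study (or aspects of the study) by their clinician".

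The one collection that is said to go on after withdrawal is safety follow-up: investigators "should continue to report any SAEs to resolution in the CRF in accordance with the safety reporting section".

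Section 8.3 lists time to disease progression (objective 6) and "Time to disease-specific and overall mortality" (objective 7) as secondary outcomes.

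**The concern.** Loss of capacity is not a neutral reason to leave a trial. The protocol does not list its causes, but serious illness is a plausible one (stroke, dementia or terminal disease, say), and such illness can come shortly before death. A rule that ends data collection at that point loses outcomes from men whose risk is likely to be above average. Censoring is harmless only when the exit is unrelated to the later risk of the event, and that is doubtful here.

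The rule also treats the man who never objected more strictly than the man who did. A participant who asks to stop questionnaires keeps his record-based follow-up under 16.8. A participant who loses capacity and has expressed no wish is withdrawn from the study under 14.7.

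At stake are mainly the mortality and progression estimates. An analysis plan can examine how sensitive they are to informative censoring, but it cannot recover events that were never collected.

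**Working it through.** The plan states no figure on this point, so the main check is to follow one man through the text.

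**1. What is lost after a 14.7 withdrawal.**
- *Outcome CRFs.* Section 16.6 has the local team record PSA, disease status, treatment failure and death. Section 21.1 names hospital records, including biopsy and radiology reports, as source data. These items need no action from the participant, but collection stops at withdrawal.
- *SAE follow-up.* This continues, but section 18.3 limits what is collected: "Only serious adverse events considered by the site investigator to be related (possibly, probably or definitely) to any of the study procedures" and also judged unexpected. Section 18.5 keeps progression, recurrence and death from progression off the SAE form. So the safety route does not recover objectives 6 and 7.
- *Registry linkage.* Sections 9.6 and 20.1 make HES and mortality data subject to funding. Neither says that linkage survives a 14.7 withdrawal.

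**2. How the man is then analysed.** Section 19.4 censors men without treatment failure at last follow-up or last known failure-free time. Men without progression are censored at death or the last known alive date. Failures recorded before withdrawal still count. The loss therefore falls on men with no earlier event and, for men who had already failed, on later progression and death.

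**3. How many men.** The documents give no rate of incapacity. Assume a constant rate r of 0.5% to 2% a year over 3 years, roughly the funded median follow-up:

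number withdrawn = 800 × (1 − exp(−3r))

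| r per year | withdrawn by 3 years | share of 800 |
|---|---|---|
| 0.5% | 11.9 ≈ 12 | 1.5% |
| 1% | 23.6 ≈ 24 | 3.0% |
| 2% | 46.6 ≈ 47 | 5.8% |

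This ignores death as a competing event, so it errs slightly high.

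**4. Effect on power for treatment failure.** As a pessimistic case, treat these men as lost from day 0 and in addition to the 10% dropout in section 19.2. Inputs from 19.2 are 800 men, 10% dropout (720 evaluable), failure of 10% versus 20%, hazard ratio log(0.9)/log(0.8) = 0.4722 and p < 0.025, taken as two-sided.

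- Expected failures: d = (number evaluable / 2) × (0.10 + 0.20).
- Schoenfeld power: Φ(√d/2 × |ln HR| − 2.241).
- Freedman power: Φ(√d × (1 − HR)/(1 + HR) − 2.241).

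| extra men lost | d | Schoenfeld | Freedman |
|---|---|---|---|
| 0 | 108.0 | 95.1% | 93.1% |
| 12 | 106.2 | 94.8% | 92.7% |
| 47 | 101.0 | 93.7% | 91.3% |

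The fall is about 0.3 to 1.8 percentage points. These formulas give more than the approximately 88% stated in 19.2, so only the change is used here, not the level. If these exits are already part of the 10% total dropout, there is no extra loss.

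**5. Effect on mortality.** The share of deaths missed equals the share that follow a recorded loss of capacity and withdrawal. The documents give no basis for that share, so no number is offered.

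**The case against.** The strongest reply is that this is a consent policy and that its effect is small. Whether records may be read after a man loses capacity depends on the consent form and information sheet, which are not shown. Section 14.7 does not use the 16.8 label of full withdrawal, so a site might apply it as a partial one. Entrants must be fit for radical treatment and general anaesthesia, and section 7.1 reports very low prostate-cancer mortality at a 10-year median in a related trial. The assessment schedule contains no capacity check, so some men would die before any withdrawal was recorded. Much of this stands, and it limits the size of the problem. It does not change the plain wording of 14.7, and sites should not have to guess which kind of withdrawal is meant.

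A reader might infer more than the documents support:

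- **That 14.7 contradicts the synopsis or the intention-to-treat rule.** It does not. The synopsis gives the general duration of follow-up, and any withdrawal rule qualifies it. Section 19.5 concerns allocation ("This means that patients will be analysed as they are randomised irrespective of the treatment actually received") and does not promise complete follow-up.
- **That these men are counted as alive and failure-free to the end of the study.** Section 19.4 censors at the last known time and does not carry them forward.
- **That the co-primary is materially damaged.** A man terminally ill from prostate cancer will usually have failed already, and that failure counts.
- **That the treatment comparison is biased.** Nothing in the documents suggests that loss of capacity differs between arms.
- **That the loss can be projected to 15 years.** That follow-up is subject to further funding, and a simple projection would ignore death as a competing event.

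**Conclusion.** The point holds as a cheap improvement to the data-collection rule. Followed as written, 14.7 and 16.8 stop collection of failure, progression and death in men who lose capacity, and no other stated route recovers those outcomes with certainty. The exit is plausibly related to prognosis, so the censoring may be informative. The main loss is in secondary objectives 6 and 7. On an assumed 0.5% to 2% a year, about 12 to 47 of 800 men would be affected by 3 years. The effect on the treatment-failure co-primary and its power is likely small over the funded follow-up. The conclusion rests on the plain reading of 14.7 as withdrawal from the whole study and on the assumed rate. The size of any bias in mortality cannot be derived from the documents.

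**What to change.** Reword section 14.7 so that loss of capacity is recorded as a partial withdrawal under the existing 16.8 categories:

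- Questionnaires and study-specific procedures stop.
- Routine-record outcome data (PSA, imaging, further treatment, failure, progression) and date and cause of death continue to be collected, where the man's prior consent and ethics approval allow and he had not objected.
- The consent form gains a matching sentence.
- Where consent does not cover this, the man is censored at withdrawal and the number of such men is reported by arm.

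The cost is one paragraph, one consent-form sentence and an ethics amendment, with no new visits or tests. The downside is that it may not apply to men already enrolled. With recruitment planned over 5 years, an earlier amendment covers more participants.
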